3.5 Primary endpoint

The WHO proposed (https://www.who.int/blueprint/priority-diseases/key-action/COVID-19_Treatment_Trial_Design_Master_Protocol_synopsis_Final_18022020.pdf) a slight modification of a preexisting COVID-19 ordinal endpoint, adding an extra status relevant only to prevention trials (no disease), and adding an extra status to reflect the difference between simple invasive ventilation and invasive ventilation plus additional organ support (ECMO, CRRT, or vasopressors). In the interest of synchronization, we will collect data to allow comparison with either the WHO or NIAID version of the scale. For analysis purposes, our primary endpoint is the WHO COVID Ordinal Outcomes Scale at day 14 (with the recognition that no patients are expected to have the status of never having developed a respiratory illness). The details of the endpoint are displayed in Table 1.

Table 1. WHO COVID Ordinal Outcomes Scale *		
Patient State	Descriptor	Score
Ambulatory	No limitation of activities	1
	Limitation of activities	2
Hospitalized, mild disease	No oxygen therapy	3
	Oxygen by mask or nasal cannulae	4
Hospitalized, severe disease	Non-invasive ventilation or high-flow oxygen	5
	Invasive mechanical ventilation without other organ support	6

	Invasive mechanical ventilation with other organ support (e.g., ECLS, CRRT, vasopressors)	7
Death	Dead	8

ECLS: extracorporeal life support; CRRT: continuous renal replacement therapy
*The score for the day reflects the worst status for the given calendar day

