Note: if the clinical attending physician believes that bacterial pneumonia is likely and requires a second antibacterial agent for "atypical" infection (an uncommon occurrence in COVID-19), patients may receive another agent (e.g., doxycycline or levofloxacin) as appropriate at the clinician's discretion.

5.2.2. Azithromycin. Patients in the azithromycin arm will receive azithromycin 500mg on day 1 plus 250mg daily on days 2-5 (may be administered IV per clinician preference).

5.3 Study Assessments. Coordinators and/or data queries will classify the COVID Ordinal Outcomes Scale on days 1–7, 14. They will also review for adverse events, including especially rash, self-report of visual changes, or symptomatic hypoglycemia. They will ensure that an EKG is performed at 24 to 48 hours post-randomization time. If a clinical EKG is not performed during this timeframe, a research EKG will be performed. In addition, ventilator status and ICU and hospital stay (using the last-off method) will be used to determine ventilator- and ICU-free days at 28 days using the worst rank ordinal technique, whereby death is scored as -1 days. In addition, coordinators and/or data queries will classify the COVID Ordinal Outcomes Scale on day 14. If this cannot be determined from the medical record, the patient will be contacted via telephone, mail, or electronic methods to determine their status on day 14.

5.2.4 Six-month assessment. A brief visit will ascertain the EQ-5D-5L to measure quality of life. Mortality and readmissions will also be assessed at that visit, which may be performed by telephone, electronic means, or in-person, depending on the subject's needs and preferences.

5.4 Approach to potential risks. Hydroxychloroquine has been used in many thousands of patients as an anti-malarial agent and in systemic lupus erythematosus and rheumatoid arthritis as a mild anti-inflammatory agent. The safety has been well established. Azithromycin has been used in millions of patients and is effective against the causes of bacterial pneumonia. Its immunomodulatory effects are also of interest in a variety of syndromes. While both agents have known side effects, such side effects are generally rare and well-tolerated.

This pragmatic study protocol is designed to optimally protect patients against risk through careful choice of exclusion criteria, pragmatic monitoring for common adverse events, and careful oversight by a DSMB.

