Secondary Analyses. We will apply similar Bayesian proportional odds models to evaluate the effectiveness of the hydroxychloroquine vs. azithromycin interventions for efficacy analyses of all ordinal outcomes. We will also present numbers (proportions) of patients in each ordinal status for all endpoints for descriptive purposes and to assist with future meta analyses. If the graphical diagnostics (described above) indicate that the proportional odds model is untenable for certain outcomes, we will report that fact, and supplement the primary analysis using the proportional odds model with separate logistic regression for different cutpoints or quantile regression in order to fully characterize the relationship of each outcome with treatment assignment.

Ordinal secondary outcomes include ventilator-, ICU-, and hospital-free days through day 28 (with death assigned as a worst-rank ordinal level^{5,6} to avoid survivorship bias for each of these outcomes). We will use the last-off method—only time after the last liberation from, e.g., ventilation counts toward the total number of -free days. Similar to the primary outcome measured at 14 days, we will apply a primary proportional odds model similar to that used for the primary analysis at day 14 to evaluate the effect of the randomized treatments on the COVID Ordinal Outcomes Scale at day 7. We will present the results of each of these analyses as the posterior median odds ratio with 95% credible interval under the moderately skeptical Bayesian prior described above. For ease of use for investigators performing meta-analyses, we will include detailed descriptions including number of patients for each value of the endpoints by treatment group as tables in the online supplement.

We include two time-to-event endpoints, censored at 28 days: time to a 1-point decrease in the COVID Ordinal scale and time to recovery (defined as in the ACTT-1 trial). The time to recovery endpoint was added after publication of the methods paper but before unblinding of investigators. It was added to assist with future meta analyses given increasing interest in it as an endpoint. Both time-to-event endpoints will be displayed by treatment group (for descriptive purposes) as Kaplan-HAHPs SAP

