Meier curves. Patients who die prior to day 28 are assigned an artificial follow-up time of 28 days censored at that point. This will assign to these patients a worse outcome than any surviving patients, and avoid conflating prolonged hospitalization with death. Descriptively, these time-to-event endpoints will be displayed as median (IQR). If fewer than half of patients meet the event before censoring, we will choose an appropriate quantile (e.g., first quartile) for description and display the proportions with events during the respective weeks of follow-up. For the sake of consistency, we will use the same ordinal regression model with the same prior distribution for the odds ratio as was used for the primary analysis to generate median posterior odds ratios and credible intervals for these endpoints.

Sub-groups. On a purely exploratory level, we will summarize effect variation in sub-groups defined by (a) age \geq 65 years, (b) symptom duration \geq 10 days, (c) in ICU at enrollment, (d) presence of at least one comorbidity, (e) race/ethnicity, and (f) receipt of any clinical azithromycin before enrollment. At early interim analyses, the sample size will be too small to support meaningful statistical inference, and we will limit presentation of results in sub-groups to descriptive summaries using the summary measures described for each outcome above.

Missing Data. We expect fewer than 5% of subjects will have missing data on either the primary or key secondary outcomes listed above. Hence, our primary analyses will be restricted to non-missing observations, without imputation. For the primary outcome, a sensitivity analysis will be performed by applying single imputation. Where daily COVID Ordinal Outcomes Scale scores are missing after hospital discharge, we will use last carried forward with the following modifications—patients discharged to a facility other than home will be classified as “home with limitations” (score 2), and patients found subsequently to be home with limitations will be rated as “home with limitations” from hospital discharge through that follow-up point. Patients who are discharged to home and found to have no limitations at day 14 will be rated as “home without” limitations starting at the time of hospital HAHPS SAP

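### For a missing post-discharge score, the SAP's imputation rule gives level 2 to any patient sent to a facility, even one moved to another hospital or still on ventilatory support

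*SAP*

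**What the plan says.** The rule is in the SAP's Missing Data paragraph. That paragraph first sets the main approach: "our primary analyses will be restricted to non-missing observations, without imputation". It then adds: "For the primary outcome, a sensitivity analysis will be performed by applying single imputation". The fill-in rules follow. They open with a condition, "Where daily COVID Ordinal Outcomes Scale scores are missing after hospital discharge, we will use last carried forward", and then modify it. The modification at issue is that "patients discharged to a facility other than home will be classified as" at home with limitations, score 2. The type of facility and the respiratory support at departure play no part. Neither document defines a facility, or separates discharge from transfer.

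In the protocol's Table 1 (section 3.5), level 2 is an ambulatory patient with "limitation of activities". Oxygen by mask or cannula is level 4, non-invasive ventilation or high-flow oxygen is 5, and invasive ventilation is 6, or 7 with other organ support. Levels 3 to 7 all carry a hospitalized label.

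The SAP also lists "time to a 1-point decrease in the COVID Ordinal scale" among its time-to-event endpoints (Secondary Analyses), and promises displays of the scale for each day from 0 to 14 (General).

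**The concern.** Carrying the last score forward would keep a transferred patient at the level last seen. The facility branch replaces that level with a nearly best one because of destination alone. For someone moved to another hospital or a ventilator unit, level 2 does not describe the patient's state. The reason the SAP gives for its post-discharge rules is that limitations are unlikely to resolve and recur by day 14. That reason concerns patients at home and does not support the facility branch.

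The sensitivity analysis should show whether missing scores among sicker survivors could change the answer. For these patients it assumes a favourable outcome, so it cannot. If the same filled scores fed the time to a 1-point decrease, leaving the study hospital on support would itself register as improvement.

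**Working it through.** The plan gives no figure for this rule, so there is none to reproduce. The check has three steps.

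**1. Displacement per patient** (levels from protocol Table 1; displacement = last level − 2)

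| Last level | Carried forward | Under the rule | Levels better |
|---|---|---|---|
| 4 | 4 | 2 | 2 |
| 5 | 5 | 2 | 3 |
| 6 | 6 | 2 | 4 |
| 7 | 7 | 2 | 5 |

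Each of these would meet a 1-point decrease wherever the filled score is used.

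**2. Which analyses the rule reaches**

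- Day-14 primary analysis: not reached. It uses observed scores only.
- Day-14 single-imputation sensitivity analysis: reached.
- Daily displays: unclear. Protocol Appendix 1 schedules the scale on days 1–7 and 14 for everyone, but on days 8–13 only for patients still hospitalized on day 14. For patients who have left, those days are missing by design. The SAP promises a display for each day without saying how the gaps are filled.
- Time to a 1-point decrease: unclear, for the same reason.
- Day-7 scale: scheduled for all, so not missing by design. The SAP defers imputation rules for secondary endpoints and places them in sensitivity analyses.

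**3. Size in the sensitivity analysis**

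Inputs:
- SAP Scenario 3, the average of the uniform distribution and Scenario 2: 0.0625, 0.2425, 0.1425, 0.1775, 0.0875, 0.0725, 0.0725, 0.1425 for levels 1 to 8.
- 0.95 × 150 = 142.5 per arm, taken as 142.
- Identical arms, so the odds ratio (OR) is 1.00.
- SAP prior for log OR: mean 0, SD 0.354.
- Number of patients rescored: an assumption, since the documents give none.

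The unadjusted proportional-odds model, logit P(Y > k) = a_k + b × (hydroxychloroquine) with OR = exp(b), is fitted by maximum likelihood to the expected counts after moving patients to level 2. With the SAP's normal approximation and a fitted standard error of 0.209, the prior weight factor is w = 0.354² / (0.354² + 0.209²) = 0.1253 / 0.1690 = 0.74. The posterior mean is w × log OR, the posterior SD is √w × 0.209 = 0.180, and P1 = Φ(−mean / SD).

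| Patients rescored to level 2 | OR | P1 |
|---|---|---|
| None | 1.00 | 0.50 |
| Five from level 6, split 3:2 | 0.976 | 0.54 |
| Three from level 6, one arm | 0.93 | 0.62 |
| Five from level 6, one arm | 0.88 | 0.69 |
| Three from level 4, one arm | 0.955 | 0.58 |
| Five from level 4, one arm | 0.926 | 0.62 |

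Example, fourth row: log OR = −0.123, mean = 0.74 × (−0.123) = −0.091, P1 = Φ(0.091 / 0.180) = Φ(0.51) = 0.69.

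The larger share, or all, of the moves is placed in the hydroxychloroquine arm. Placing it in the azithromycin arm inverts the OR (1 / 0.884 = 1.13 for the fourth row).

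For scale, the SAP states: "We expect fewer than 5% of subjects will have missing data", which is fewer than 0.05 × 300 = 15. Suppose all 15 were facility patients at level 4, with 150 per arm. An equal split leaves the OR at 1.00. A 10:5 split gives 0.93 or 1.08, and all 15 in one arm gives 0.80 or 1.25. Nothing in the documents suggests numbers like these.

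**The case against.** The strongest reply is about scope. The rule does not score every patient discharged to a facility as level 2, although a reader might infer that from the clause alone. It applies only where a post-discharge score is missing, and an observed score, including death, stands. The protocol limits such gaps at day 14: "If this cannot be determined from the medical record, the patient will be contacted via telephone, mail, or electronic methods" (section 5.3). That stands, and the primary result is not biased by this rule.

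A reader might also infer that transfers will count as events in the time to a 1-point decrease, or will enter the day-7 model. The documents do not say so. What they show is silence about where filled scores are used.

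Third, level 2 has a rationale. It is the worst level for a living patient outside hospital, so it is conservative against level 1. A nursing-facility patient on low-flow oxygen has no level of their own, and keeping that patient at 4 while someone at home on oxygen can only be 1 or 2 would create a new inconsistency. This stands for low-flow oxygen. It does not cover a move to another hospital or a patient still on ventilatory support. Those cases are possible under the wording, but no document records one.

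Fourth, the rule is the same in both arms, so one-arm placement is an extreme. Under Scenario 2, level 6 holds only 0.02 × 142 = 2.84 patients per arm, so five from one arm could not arise in expectation; Scenario 3 has 0.0725 × 142 = 10.3. The 142 also represents patients with observed scores, whom the rule cannot reach. The figures therefore illustrate the contrast between the rule and carrying forward, and do not predict a shift. Even P1 = 0.69 is far from the SAP's 95% threshold.

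Finally, this should not be called the trial's only missing-data sensitivity analysis. Protocol section 5.7 names multiple imputation using earlier scale scores. The SAP names single imputation instead, without expressly withdrawing the other.

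**Conclusion.** The concern holds in a narrow form. For a missing post-discharge score, the facility branch assigns level 2 whatever the type of facility or support at departure, which is 2 to 5 levels better than carrying forward a level of 4 to 7. It weakens the single-imputation sensitivity analysis of the day-14 outcome and leaves the complete-case primary analysis alone. An effect on the daily displays and the time to a 1-point decrease is conditional on filled scores being used there.

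For five level-6 patients, the illustrative shift from an OR of 1.00 runs from about 0.98 (split 3:2) to about 0.88 (all in one arm, the upper bound for that number). With an equal split there is essentially none. This rests on the assumed count, the Scenario 3 distribution, identical arms and no covariate adjustment. It calls for a correction of wording and does not threaten the main conclusion.

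**What to change.** Amend the Missing Data paragraph of the SAP:

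1. Define discharge as distinct from transfer, and define facility.
2. Limit score 2 to discharge to a non-hospital facility without ventilatory support at departure.
3. For transfer to a hospital-level facility, or departure with ongoing non-invasive, high-flow or invasive support, carry the last observed level forward until status is ascertained.
4. Do not count the transfer itself as a 1-point decrease.
5. State one convention for low-flow oxygen outside hospital, and apply it equally to home and facility discharges.
6. State which analyses use the filled daily scores: the day-14 sensitivity analysis only, or also the daily displays and the time to a 1-point decrease.

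The cost is SAP wording, plus a check of discharge destination and last-day support in records already reviewed. The change should be made by blinded personnel, as the SAP says of its own drafting.

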2.0 Study Summary

2.1 Study Title: Hydroxychloroquine vs. Azithromycin for Hospitalized Patients with Suspected or Confirmed COVID-19 (HAHPS).

2.2 Study Objective: Assess the efficacy and safety of hydroxychloroquine (HCQ) as opposed to azithromycin for suspected or confirmed COVID-19.

2.3 Study Hypothesis: Hydroxychloroquine is superior to azithromycin in improving outcomes among patients with suspected or confirmed COVID-19.

2.4 Study design: Phase 2 prospective, randomized, open-label active comparator trial.

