7.2 Serious Adverse Events

Serious adverse event collection begins after the patient or LAR has signed informed consent and has received study drug or undergone study procedures. If a patient experiences a serious adverse event after consent, but prior to receiving study drug, the event will NOT be collected unless the investigator feels the event may have been caused by a study procedure.

Investigators must alert the DSMB of any **serious and study drug or study procedure related** adverse event within 24 hours of investigator awareness of the event. Alerts issued via telephone are to be immediately followed with official notification on the adverse event case report form. See Appendix 4 for reporting timelines for serious, unexpected, study related events (SAEs) and serious, unexpected suspected adverse reactions (SUSARs).

As per federal definitions (primarily in 21 CFR 312.32(a)), a **serious** adverse event is any adverse event that results in one of the following outcomes:

- Death
- A life-threatening event, one that places the subject at immediate risk of death (this does not include an event that, had it been more serious, would have placed the subject at immediate risk of death)
- Prolonged inpatient hospitalization or rehospitalization
- Persistent or significant disability/incapacity, indicating a substantial disruption of a person's ability to conduct normal life functions (i.e., the adverse event resulted in a significant, persistent or permanent change, impairment, damage or disruption in the patient's body function/structure, physical activities and/or quality of life).

Important medical events that may not result in death, be life-threatening, or require hospitalization may be considered serious adverse events when, based upon appropriate medical judgment, they may jeopardize the patient and may require medical or surgical intervention to prevent one of the outcomes listed in this definition.

Serious adverse events will be collected during the first five days, regardless of the investigator's opinion of causation. Thereafter, serious adverse events are not required to be reported unless the investigator feels the events were related to study drug or a protocol procedure.

APPENDICES

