Official Title: Hydroxychloroquine vs. Azithromycin for Hospitalized Patients With Suspected or Confirmed COVID-19 (HAHPS): A Prospective Pragmatic Trial

NCT #: NCT04329832

Document Date: Jun 29 2020

Responsible analytic personnel

[name]
Professor of Medicine and Epidemiology
University of Utah

[name], MStat
Biostatistician, Intermountain Medical Center

[name]
Biostatistician, Intermountain Medical Center

Responsible investigators

[name]
Associate Professor of Medicine
Intermountain Medical Center/University of Utah

[name], DO
Physician investigator
Intermountain Medical Center

[name]
Professor of Medicine
University of Utah

[name]
Assistant Professor of Medicine
Intermountain Medical Center

Table of Contents

BACKGROUND	2
SUMMARY OF ANALYTIC APPROACH	3
General	3
Analysis Sets	3
Primary Analysis	4
Secondary Analyses	7
Sub-groups	8
Missing Data	8
Safety reporting	9
Concomitant medications	11
Interim Monitoring	12
Sample size and power	12

Background

The HAHPS trial is a randomized, open label, active comparator trial of hydroxychloroquine vs. azithromycin for hospitalized patients with COVID-19. The HAHPS trial enrolled patients admitted to the hospital with suspected or confirmed COVID-19. As outlined in the protocol and a prior publication,¹ the eligibility criteria excluded patients with markers of increased risk associated with administration of hydroxychloroquine or azithromycin. The trial is being conducted at Intermountain and University of Utah hospitals. While the trial is open-label, outcomes assessors and investigators are blinded to outcomes by treatment group. This SAP was written by blinded personnel, without knowledge of study outcomes.

Summary of analytic approach

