discharge. This approach will be used because persisting limitations are unlikely to have resolved and then recurred by 14 days. Similar single imputation rules will be devised for sensitivity analyses of secondary efficacy endpoints consistent with prior practice in the field and will be determined before the given analysis is performed to avoid bias from knowledge of outcomes.

Safety reporting

The HAHPs trial uses the adverse event reporting developed for the PROWESS-SHOCK trial.^{7,8} This approach is based on the high incidence of conditions resulting from the underlying disease that would be classified as adverse events if they occurred in healthy outpatients but are unlikely to be related to the study drug. Instead of being classified as adverse events, such events are monitored as study clinical or safety outcomes (Table 2). The exception to this rule are events which are either serious and study-related or which lead to permanent discontinuation of study drug. Those latter are reported as adverse events and are classified within the MedDRA taxonomy.

For reporting purposes, for each safety outcome or adverse event each patient will be classified as having experienced the outcome at least once (vs. never having experienced the outcome). We will separately provide counts (proportions) of safety outcomes and individual adverse events. In early interim analyses, comparisons of safety outcomes between treatment groups will be viewed as primarily descriptive. However, we will provide nominal p-values to compare adverse events and safety outcomes between groups without multiple comparison adjustment using the Chi square or Fisher exact test as appropriate to provide a crude assessment of the compatibility of observed differences between treatment groups with chance. Isolated p-values which are < 0.05 will be interpreted recognizing that 5% of such p-values will reach this threshold by chance in the absence of an actual effect of the treatment.

QTc was monitored at 24–48h after randomization as a study procedure. QTc monitoring at baseline was not mandatory but was described where it was available. We also described the change between baseline and 24–48h after randomization in QTc. These results will be summarized HAHPs SAP

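### Attribution made with the arm known decides which events enter the tested adverse-event list and the death row, and possibly the other Table 2 rows; no any-cause comparison is assured

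*SAP*

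**What the plan says.** Protocol 2.4 describes a "Phase 2 prospective, randomized, open-label active comparator trial". The SAP Background adds: "While the trial is open-label, outcomes assessors and investigators are blinded to outcomes by treatment group". That statement is about results by group. It does not hide a patient's assigned drug from the person judging causation.

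On conditions that commonly arise from the underlying disease, the SAP (Safety reporting) says: "Instead of being classified as adverse events, such events are monitored as study clinical or safety outcomes (Table 2". It then makes an exception: "The exception to this rule are events which are either serious and study-related or which lead to permanent discontinuation of study drug". Exception events are reported as adverse events and coded in MedDRA. Table 2 itself restricts its death row to deaths not attributed to drug or procedures. None of its other rows carries a causation qualifier.

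On analysis, the SAP says "We will separately provide counts (proportions) of safety outcomes and individual adverse events" and "we will provide nominal p-values to compare adverse events and safety outcomes between groups without multiple comparison adjustment". Its only interpretive caution is that about 5% of such p-values fall below 0.05 by chance.

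Protocol 7.1 and Appendix 4 (A4.3) give the investigator's view of relatedness a deciding role in lifting the exemption of study-specific outcomes from adverse event reporting. Protocol 7.2 says "Serious adverse events will be collected during the first five days" whatever their cause.

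**The concern.** If two arms have the same number of arrhythmias or seizures, a safety table should show no difference beyond chance. Here, whether an event enters the adverse-event list depends partly on what a clinician who knows the arm believes about the drug, or on a decision to stop that drug for good. If one drug's events are attributed more readily, that arm gains adverse events without any difference in event rates. If those events also leave Table 2, the same arm loses safety outcomes, so the two tables point in opposite directions.

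The SAP's caution about 5% chance findings does not cover this, because unequal attribution is systematic. Protocol Appendix 4 has the DSMB review adverse events and clinical outcomes at interim analyses. The SAP (Concomitant medications) also reuses the safety outcomes to describe patients by drugs actually received. A distorted row would carry into both.

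**Working it through.** **Inputs from the documents.** Target of 300 randomized (Protocol 5.8; SAP, Sample size and power). Chi-square or Fisher exact test, with nominal threshold 0.05 (SAP, Safety reporting).

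**Assumed, because the documents do not give them.** 1:1 allocation with everyone dosed, so 150 per arm; the same true event rate *r* in both arms; a share *s* of events that are serious; attribution shares *f* for hydroxychloroquine (H) and azithromycin (A). The discontinuation route is left out.

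**The plan's own figure first.** With equal rates and no routing, exact enumeration over two binomials (chi-square, or Fisher when an expected count is below 5) gives p<0.05 with probability 0.047 to 0.052 for event rates of 5% to 40%. The SAP's 5% is reproduced.

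**Formulas with routing.**
- Adverse-event row rate in an arm: *r·s·f*.
- Safety row rate, if attributed events leave it: *r·(1 − s·f)*.
- Rejection probability: the sum of Bin(a; 150, p_H) × Bin(b; 150, p_A) over all pairs (a, b) with two-sided Fisher p<0.05.

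Example, *r* = 0.20, *s* = 1, *f* = 0.50 vs 0.20. Safety row: 150 × 0.20 × 0.50 = 15 vs 150 × 0.20 × 0.80 = 24 expected. Adverse-event row: 150 × 0.20 × 0.50 = 15 vs 150 × 0.20 × 0.20 = 6.

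| *r* | Serious | Attributed H vs A | Safety row rates | p<0.05 | AE row rates | p<0.05 | Counted together |
|---|---|---|---|---|---|---|---|
| 20% | all | 50% vs 20% | 10% vs 16% | 28% | 10% vs 4% | 45% | 4% |
| 20% | all | 30% vs 10% | 14% vs 18% | 12% | 6% vs 2% | 30% | 4% |
| 20% | all | 30% vs 20% | 14% vs 16% | 6% | 6% vs 4% | 7% | 4% |
| 20% | half | 30% vs 20% | 17% vs 18% | 4% | 3% vs 2% | 3% | 4% |
| 10% | half | 50% vs 20% | 7.5% vs 9% | 5% | 2.5% vs 1% | 5% | 3% |

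Fisher is conservative, so its baseline is 3–4% rather than 5%. With chi-square where expected counts allow, the 30% vs 10% line becomes 16% and 40%, against 5% counted together.

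**The two readings of Table 2.** If attributed events leave their row, both rejection columns apply. If they stay, each non-fatal safety row reverts to the last column; only the adverse-event list and the death row remain affected.

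**Relatedness thresholds side by side.** Protocol 7.1 requires an event to be serious and definitely or possibly related. A4.3 lifts the exemption for related or uncertain events without mentioning seriousness, but for death names only definite or probable relation. The SAP uses seriousness with study-relatedness, or permanent discontinuation. Under these texts the same event can land on different lists.

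**The case against.** The strongest reply is that exclusive counting is an inference. The SAP says exception events are reported as adverse events; it does not say they are deleted from Table 2. Those outcomes are measured daily for five days and each patient is classed as ever or never having one. Only the death row mentions causation, so the rest may already be any-cause. This stands, and it limits what is certain to the adverse-event list and the death row.

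A reader might also infer that equal event rates will routinely look different. The documents do not support that: they give no attribution shares, many Table 2 events need not be serious, and MedDRA coding thins the adverse-event rows. The table shows little or no inflation for small gaps or less frequent, partly non-serious events.

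Nor do the documents support inferring a bias against hydroxychloroquine. Coordinators do review for adverse events "including especially rash, self-report of visual changes, or symptomatic hypoglycemia" (Protocol 5.3), and Protocol 5.4.1 lists visual impairment and hypoglycemia for hydroxychloroquine only. But rash and QTc prolongation are listed for both drugs, and *C. difficile* and abnormal liver function for azithromycin only.

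There is partial cover. Death and ventilation enter the ordinal scale and the free-day endpoints, QTc is compared directly, and the QTc stopping rule is partly objective. Appendix 4 has the principal investigator assess serious-event causation with the DSMB, though neither document says this is done without knowledge of the arm. The p-values are called nominal and crude, with no stated decision rule attached. None of this assures an any-cause comparison of arrhythmia, seizure, hypoglycemia, visual changes or liver tests.

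**Conclusion.** The concern holds in a limited form. Two tested quantities depend on attribution made with the arm known: the adverse-event list and the death row. The remaining Table 2 rows join them only if the SAP's wording means that attributed events leave those rows, which it leaves open. The possible effect runs from none to a false-signal rate of about 28% in a safety row and 45% in an adverse-event row, with Fisher's test and 150 per arm. The upper figures need a common, mostly serious event and a large attribution gap; all the shares are assumptions. Any-cause counting returns the rate to 3–4% whatever the split. Because a stated rule creates the dependence and the remedy is cheap, the plan should be changed, but this does not show that the trial's safety results are biased.

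**What to change.** In the SAP (Safety reporting and Table 2):

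1. State that every Table 2 event is counted in its row, by arm, regardless of attributed cause or discontinuation.
2. Change the death row to all-cause death.
3. Attach p-values to these any-cause rows only.
4. List related adverse events and discontinuations descriptively by arm, without p-values.
5. Reconcile the relatedness thresholds in Protocol 7.1, Appendix 4 (A4.3) and the SAP.

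Do not add a test of all serious adverse events through day 5 as things stand. Protocol 7.2 collects them whatever their cause, but 7.1 and A4.3 exempt study-specific outcomes unless judged related, so that set may itself depend on attribution. Those sections must be reconciled first.

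The cost is SAP wording and a recount of events already monitored daily. If some attributed events were recorded only on the adverse event form, they would have to be mapped back to their Table 2 row within the five-day window. An attributed event will appear in both tables, which needs a footnote.
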